This trial aims to deliver, across a range of UK hospitals, a package of interventions for Acute Kidney Injury (AKI) aimed to improve recognition and quality of care for AKI, and to assess how this translates into better outcomes in AKI patients and if this intervention can reduce the incidence of h-AKI (detailed protocol available on request).

For practical reasons this service can only be applied at the level of the population covered by the hospital and not on a subset of random patients within a hospital. Also the intervention is assumed to have a positive effect on AKI management/outcomes. For these reasons the study has been set up as a stepped-wedge cluster randomised trial (SWCRT), with the intervention applied at a cluster level and applied to all participating units by the end of the study. Such an approach overcomes any ethical problem of withholding a treatment considered likely to be effective, as the entire population recruited will receive the treatment by the end of the study. This approach also allows for differentiation between the effect of the intervention and potential independent unknown time-related factors.

There are no reporting guidelines specific to SWCRTs, so this Statistical Analysis Plan (SAP) is written to be consistent with the extension to cluster randomised trials of the CONSORT 2010 document [Campbell et al., 2012] and further suggestions recently published for SWCRT [Hemming et al, 2015]. This statistical analysis plan will guide the Trial Statistician during the statistical analysis of all quantitative outcomes in order to answer the objectives of the study.

STUDY DESIGN

A Stepped Wedge Cluster Randomised Trial approach will be taken. This means that the intervention will be delivered in sequential steps to one or more units of randomisation per time-period and

delivered to all the units of randomisation by the end of the study. This study has recruited 5 hospitals and is planned to take two years, between December 2014 and November 2016, with 2 initial control periods for all 5 hospitals, followed by 5 steps of randomisation (one hospital per step), and including a transition period (the first 'treatment period', when the treatment is expected not to have reached full efficacy on outcomes), for a total of 8 time-periods, each of 3 months in length (24 months in total – see Table-1, page.6).

THE INTERVENTION

The intervention (protocol, sections 3 and 5, available on request for details), has 3 parts:

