- An AKI electronic detection system within pathology laboratory software
- An educational program to raise awareness and knowledge of AKI in care workers at hospital
- An AKI care bundle

The AKI electronic detection system has already been mandated at a national level (England only), with the plan to start nationwide from April 2015. The 5 hospital recruited for this SWCRT have been exempted from the initiative for the time being, so they would be able to wait to implement the intervention at their assigned time of randomisation, while having the electronic detection system in place since the end of 2014, but silent (as to measure the incidence of AKI during the baseline periods, with no active intervention).

OUTCOMES MEASURES

The outcomes of this study will be measured for all adult patients hospitalised overnight in the 5 participating hospitals, and identified as having an episode of AKI while in hospital by the pathology laboratory detection system (with results suppressed, non-visible to end-users, during control periods). The outcomes will be measured for the entire length of the study-period (1st Dec 2014 to 30th Nov 2016) for all of the AKI events, so multiple entries per patient are possible.

Primary outcome

- Thirty-day mortality after an episode of AKI. These are patient level data, binary outcome (0=patient alive 30 days after the AKI episode; 1=patient dead 30days after the AKI episode, logistic analysis).

Secondary outcomes

- 1. Incidence of h-AKI (aggregate data, counts, number of h-AKI cases, defined as AKI developed after >24hrs in hospital, with the denominator at risk being the total overnight hospitalisation episodes, Poisson analysis, standardised).

- 2. Incidence of AKI progression (defined as AKI that increases by at least one stage of AKI from AKI-stage at time of first detection) during hospitalisation. These are patient level data, binary outcome for each episode of AKI (0=did not progress during hospitalisation; 1=progressed during hospitalisation, logistic analysis).
As we will not be able to determine for all patients diagnosed with level-3 AKI if they progress to need of acute dialysis during hospitalisation, we will perform this analysis to the cohort of AKI level-1 and level-2 episodes only.
- 3. Incidence of individual AKI stages (stage 1, stage 2 and stage 3). These are aggregate data, counts, to analyse as secondary outcome n-1.

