The annual number of hospital admissions in the 5 institutions recruited was taken from HSCIC (total annual admissions of about 434,000). We used a conservative assumption of AKI incidence of 2.5% of admissions and 30-days mortality rate after AKI of 16% [Selby 2012], which corresponds to an average of AKI episodes per hospital per 3 months of about N=540. Power was set at 80%, alpha at 0.05 and a range of values for inter class correlation (ICC) between 0.01-0.2 was considered. For the sample size calculations we used a Stata program [Hemming and Girling, 2014], which can accommodate for the transition periods. This showed that with a trial study-time of two years (Dec'14 – Nov'16) using the 5 units, with one unit per randomisation step and with one transition period (as in table-1), we would be able to detect a decrease in mortality from 16% to 12.8%. This corresponds to a reduction of about 20% in 30-days mortality, which is both clinically relevant (equating to around 300 fewer deaths each year for the total of the 5 units) and plausible.

RECRUITMENT AND RANDOMISATION

- Eligibility of hospitals

Considering this trial was starting in parallel to the AKI national program (with the need to temporarily exempt the hospitals recruited) and the knowledge that the numbers of AKI episodes in hospitalised patients are fairly high, we planned to limit the recruitment to only 5 hospitals. For convenience the following 5 units were recruited, 2 from Surrey (Ashford and Frimley Park) and 3 from Yorkshire (Bradford, Leeds General and Leeds St. James).

- Eligibility of patients

Adult patients (≥ 18 yrs) hospitalised overnight in the participating hospitals are eligible if they should present in hospital with AKI or develop an episode of h-AKI, during the study period. In particular, AKI will be identified by having an inpatient blood test that triggers an AKI warning stage result, using the NHS England AKI detection algorithm (<http://www.england.nhs.uk/wp-content/uploads/2014/06/psa-aki-alg.pdf>), both in the control/baseline periods (when results are suppressed, not visible to end-users) and implementation periods.

Patients that are identified as having AKI but were already on chronic dialysis are not eligible and will need to be excluded, while patients with a renal transplant are eligible.

The five hospitals were recruited and the randomisation took place on the 11th of May 2015.

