Randomisation was performed using SAS-9.3 (RANUNI function), to generate 5 random numbers.

These were then allocated to the five hospitals (listed in alphabetical order, based on hospital name), and finally the hospitals were sorted based on their random numbers, from smallest to highest, giving the sequence of randomisation.

DATA SOURCE, COLLECTION AND VALIDATION

Data from hospitals

All data used for the analyses described in this document will be collected as part of routine clinical care, from electronic hospital records. Patient level data will be extracted from the hospitals' PAS for all patients flagged by the AKI electronic detection system. The data extracted will be sent to the UKRR. If data are sent in separate files, each file will need to contain unique patient identifiers to allow subsequent linkage and removal of duplicates by the UKRR.

Data set (see <https://www.thinkkidneys.nhs.uk/wp-content/uploads/2014/12/AKI-Warning-Algorithm-Best-Practice-Guidance-final-publication-0112141.pdf> for details) will include:

- Patient identifiers and demographics:
 - NHS number or Local Patient Identifier
 - Date of birth
 - Gender (M/F/U)
 - Ethnicity (name/code)
- Date of admission and date of discharge
- Primary specialty (text field)
- Charlson co-morbidity score (numeric score) and constituent chronic disease binary scoring (1=present, 0=absent)
- In hospital mortality (numerical field, 1=died in hospital 0=survived to discharge)
- 30 day mortality (numerical field, 1=died within 30days of first AKI warning stage result 0=survived to >30days)
- Date of death (date field)
- Length of hospital stay (numerical, in days)
- ICU admission (1=admitted to ICU during hospital stay, 0=no ICU admission) and ICU admission length of stay (numerical field in days)
- AKI data (see <https://www.thinkkidneys.nhs.uk/wp-content/uploads/2015/01/Transmitting-AKI-Warning-Stage-Data-to-the-UKRR-final.pdf> for detailed specification): initial AKI warning stage (numerical field limited to 1, 2 or 3), highest AKI warning stage (numerical field limited to 1, 2 or 3), time between admission and first AKI Warning stage result (numerical field, in hours), final inpatient creatinine result to assess recovery (numerical field, micromol/l).

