- Data on population at risk: For each of the 3-months periods, the total number of hospital admissions in adult patients (≥ 18 yrs old, elective and non-elective admissions, excluding day case contacts and patient discharged directly from ED) will be needed to estimate the population at risk to analyse incidence of AKI. If possible, hospitals will return a file containing the full list of those admissions, without any patients' identifier, but containing age (rounded to unit), gender and ethnicity of patients. This will allow the statistician to perform a standardised analysis of AKI incidence rates, without having to pre-specify to the hospitals the level of standardisation. If this is not possible, the total number of admission should be given,

preferentially by age-group (18-<25, 25-<30, 30-<35 and so on in 5-years age-bands), gender and ethnicity (South Asian, Black, Other (including mixed race and Chinese), White and Missing).

While the hospitals are responsible for identifying and excluding patients that were in day-care or were already receiving chronic dialysis, the data item 'time between admission and first AKI Warning stage result' will allow the analysts at the UKRR to distinguish episodes of community-acquired AKI and hospital-acquired AKI. Any hospital that should not be able to automatically apply the exclusion of those patients already on dialysis will need to provide the UKRR with necessary extra variables to identify these patients.

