We will present a table with number of total overnight hospitalisation episodes in adult patients, number of episodes of AKI (and numbers of patients with AKI episodes) and number of AKI episodes with complete set of variables, by hospital, per time-period (Table-2).

Table-2. Example of how numbers of AKI episodes and data completeness could be presented

Hospital		N total overnight Hospitalisations	N episodes of AKI (N patients)	N hospitalisation with AKI and complete covariates (% of tot AKI)
A	TP_1	20,000	500 (450)	480 (96%)
	TP_2			
	TP_3	21000	580 (540) etc.	550 (95%)
	TP_4			
	TP_5			
	TP_6			
	TP_7			
	TP_8			
B	TP-1	16,000		
	TP-2	15,500		
	TP-3	16,500		
	TP-4			
	TP-5			
	etc.			

White=control; Orange=Transition; Yellow=exposed; 1 hospital per block, numbers for each time-period
 TP=time period, 1=1stDec'14-28Feb'15, 2=1stMar-31may'15, and so on

Interim analysis and data quality

No interim analysis will be conducted on the primary and secondary outcomes. However data monitoring will be done to insure that the data collected by the hospitals via PAS are in the right format a first time by March 2016 from all of the 5 hospitals, and then again every 3 months for each of the hospitals.

We will also test the matching process of patients with AKI with the RRT patients in the UKRR database a first time in March 2016 and then again at the end of the study.

The last data collection should occur around Feb-Mar'17.

Descriptive statistics

The characteristics of patients with episodes of AKI by exposure (control versus intervention) and their outcomes will be presented for each hospital. We don't expect significant differences in the demographic of the population feeding to each hospital during the 2 years study-period, and therefore the number of people presenting with AKI and needing hospitalisation is not expected to change with the intervention (as the incidence is determined by the AKI-alert activation in both baseline and exposed periods). However we hope to observe a decrease in h-AKI with the intervention, as this will hopefully increase awareness of AKI and use of protocols that minimise risks of AKI development.

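### Hospital-acquired AKI is classified by when the first warning result appears, so a change in the timing or frequency of blood testing could mimic or hide prevention, and no check for this is planned

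*SAP*

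**What the plan says.** Under Outcomes measures, secondary outcome 1 is the incidence of h-AKI, "defined as AKI developed after >24hrs in hospital", "with the denominator at risk being the total overnight hospitalisation episodes". The data set listed under Data from hospitals contains one item that can place an episode on either side of 24 hours: "time between admission and first AKI Warning stage result (numerical field, in hours". The same section says, without qualification, that this item "will allow the analysts at the UKRR to distinguish episodes of community-acquired AKI and hospital-acquired AKI". Under Eligibility of patients, "AKI will be identified by having an inpatient blood test that triggers an AKI warning stage result".

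The opening section describes a package "aimed to improve recognition and quality of care for AKI". One of its three parts is "An educational program to raise awareness and knowledge of AKI in care workers at hospital". Under Descriptive statistics the SAP holds that "the number of people presenting with AKI and needing hospitalisation is not expected to change with the intervention", because the same alert algorithm identifies AKI in baseline and exposed periods. It hopes for a fall in h-AKI, which it links to awareness and preventive protocols.

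Analysis of secondary outcomes plans cluster-level Poisson models for h-AKI and for AKI by stage. It plans none for community-acquired AKI or for total AKI, and no alternative to the 24-hour cut.

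**The concern.** The definition concerns when AKI develops, but the data record when it is first flagged. Consider a patient who arrives with AKI. If the first flagged inpatient test is at 30 hours, the episode counts as h-AKI. If it is at 10 hours, the same episode counts as community-acquired. Anything that shifts the first test across 24 hours therefore changes the h-AKI count without changing the disease.

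Running the alert silently in control periods makes the algorithm the same in both conditions. It does not make the timing or frequency of testing the same, and an intervention on recognition, with staff education, could change either. Earlier first tests would lower recorded h-AKI with nothing prevented. More tests later in the stay would find AKI that went unseen in control periods and so raise recorded h-AKI.

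Lowering h-AKI incidence is a stated aim of the trial, so this bears on how that result can be read. The SAP discusses a detection artefact only for laboratory re-organisation.

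**Working it through.** **The plan's own base figure.** Sample size calculation gives about 434,000 admissions a year in five hospitals and AKI in 2.5% of them. 434,000 × 0.025 / 5 / 4 = 542.5 episodes per hospital per quarter, which agrees with the stated figure of about 540.

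**Assumptions, not in the SAP.** The h-AKI share of AKI in control periods is h = 30%, 40% or 50%. Earlier testing re-labels a share s = 3% or 5% of all AKI episodes as community-acquired. Nothing is truly prevented.

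**Formulas.**
- h-AKI rate ratio = 1 − s/h
- community AKI rate ratio = 1 + s/(1 − h)
- total AKI rate ratio = 1
- z = ln(h-AKI rate ratio) / SE

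**Standard error.** This comes from weighted least squares on the 35 non-transition hospital-quarters, with hospital and period effects and cell weight 540 × h. Error is Poisson only. Cells before each hospital's transition are taken as control, as the text describes; Table-1 as printed codes some of them as exposed. The SE of the log rate ratio is 0.061, 0.053 and 0.047 for h = 30%, 40% and 50%.

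| s | episodes moved per hospital-quarter | h | h-AKI rate ratio | z | community rate ratio |
|---|---|---|---|---|---|
| 5% | 27 | 30% | 0.833 | -3.0 | 1.07 |
| 5% | 27 | 40% | 0.875 | -2.5 | 1.08 |
| 5% | 27 | 50% | 0.900 | -2.2 | 1.10 |
| 3% | 16 | 30% | 0.900 | -1.7 | 1.04 |
| 3% | 16 | 40% | 0.925 | -1.5 | 1.05 |
| 3% | 16 | 50% | 0.940 | -1.3 | 1.06 |

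With twofold overdispersion each z is divided by √2, and the 5% case becomes about -2.1 to -1.6.

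**A second route.** Let H be true h-AKI, C true community AKI, m the share of C first flagged after 24 hours in control periods, and r the share of those brought forward to 24 hours or earlier under exposure. The apparent rate ratio is [H + C·m·(1 − r)] / [H + C·m].

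Take a recorded share of 40%, m = 10% and r = 50%. Then C = 0.6/0.9 = 0.667, H = 0.333 and C·m = 0.067, so the ratio is (0.333 + 0.033)/0.400 = 0.92. That is 217 falling to 199 per hospital-quarter. For shares of 30-50% and m of 5-20%, the ratio runs from 0.85 to 0.99 at r = 25%, and from 0.71 to 0.97 at r = 50%. In this design a ratio of about 0.89-0.91 reaches p < 0.05. The artefact could therefore be negligible or could be declared significant.

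Both routes model earlier first testing only. More testing later in the stay would push the ratio upwards; the SAP gives nothing from which to size that.

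**The case against.** **Earlier testing as a feature of the intervention.** A reader might infer that the SAP promotes earlier testing. It does not say so. A displayed alert follows a result that has already triggered a warning, so it cannot bring that episode's first warning forward. Only education or awareness could plausibly do that, and nothing says that the education targets the first 24 hours. This stands: the change in testing is a possibility, not a documented effect.

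**A bias that always favours the intervention.** A reader might infer this from the earlier-test example. The documents do not fix the direction, because more testing later in the stay would work the other way.

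**A shift that could not be detected.** This too would be overstated. The stage-specific models of outcome 3 together cover all AKI, and under pure re-labelling with stage unchanged they would stay flat while h-AKI fell. Table-2 gives AKI episodes and overnight hospitalisations by hospital and period, and Table-3 gives the h-AKI share or incidence by exposure. The check is only partial, though. The tables are descriptive and not adjusted for time, the stage models do not separate community from hospital AKI, and the SAP does not plan any of these as a check on classification.

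**Size.** The h-AKI share and the amount re-labelled are assumed. At a 40% share, a 5% shift needs about 14% of community AKI to be first flagged after 24 hours in control periods and half of it to be brought forward. The SAP neither supports nor excludes this.

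**Conclusion.** The point holds in a limited form. The SAP defines h-AKI by development after 24 hours and identifies it by time to first warning, with no planned safeguard against testing that differs by exposure. The outcome could mislead in either direction.

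Under the stated assumptions, re-labelling 5% of AKI episodes would by itself give a rate ratio of 0.83-0.90, nominally significant with Poisson-only error. Re-labelling 3% would give 0.90-0.94, not significant alone but enough to inflate a real effect. These figures illustrate what could happen; they do not estimate what will.

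The consequence is confined to the interpretation of secondary outcome 1. The primary outcome covers all AKI episodes and does not use this cut.

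**What to change.** In the analysis of secondary outcome 1:

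1. Fit the same cluster-level Poisson model to community-acquired AKI (first warning at or before 24 hours) and to total AKI. Report the rate ratios for h-AKI, community AKI and total AKI side by side, with confidence intervals.
2. Pre-specify a sensitivity analysis with h-AKI defined as first warning after 48 hours, from the hours field already collected.
3. State that a fall in h-AKI with a matching rise in community AKI will be read as possible re-classification.

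A significant fall in total AKI should not be made a condition for concluding prevention. At a 40% share, a true h-AKI rate ratio of 0.875 lowers total AKI by only 0.40 × 0.125 = 5%. With SE about 0.053 × √0.4 = 0.034, z is ln(0.95)/0.034, about -1.5, so real prevention would be rejected.

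The cost is SAP wording and a few extra runs of an existing model, on numerators and denominators already collected. The 48-hour analysis will have fewer events and so wider intervals.

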Therefore when comparing the unexposed versus exposed patients with AKI, differences could be expected, if incidence of h-AKI should be influenced by the intervention differentially in specific subgroups of the hospitalised population (e.g. if h-AKI preventable in the younger but not in the older, then the post-intervention AKI population will be older).

Also, each hospital covers different population-mix, and while each one will contribute both control and exposed AKI-patients, they will do so in different proportions, depending on when they are randomised to the intervention. This will contribute greatly to any difference in demography between the control and the exposed groups.

Whilst we do not intend to test for differences in demography between control and exposed groups for the full cohort, we will adjust the analyses for the covariates described because of the potential imbalance across hospitals and across steps.

We will present categorical variables as numbers and percentages. Continuous variables will be presented using mean and standard-deviation, or median and interquartile range, depending on their distribution (see Table-3).

Table-3

Hospital	Variable	Control	Exposed
A	N episodes (N patients) % male Ethnicity age-group comorbidity score % AKI levels (1-2-3) % h-AKI over total AKI (or incidence of h- AKI) N deaths by 30days Length hosp-stay (median-IQR) N Critical care (% >0) N recovered (%) N progressed (%)		
B etc	N % male Ethnicity age-group		

More detailed graphical representation of the primary outcome (30 day mortality) will be given (see Figure-1 for example). Summary results of secondary outcomes will also be presented in graphical or table format.

[figure not shown]

Figure-1. Example of graphical presentation of 30-days mortality data for hospitals A and B, where empty symbol=control, pattern symbol=transition, full symbol=exposed).

Analysis of primary outcome

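### The plan recognises that the intervention may change who is counted as having AKI, but pre-specifies no mortality analysis robust to that change

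*SAP*

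**What the plan says.** **Entry to the analysis.** Under Eligibility of patients, "AKI will be identified by having an inpatient blood test that triggers an AKI warning stage result". The same algorithm runs in both phases, with results hidden from users during control periods.

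**Expected effect on the AKI group.** Descriptive statistics says that "the number of people presenting with AKI and needing hospitalisation is not expected to change with the intervention", on the ground that the same alert identifies cases before and after. The next sentence adds that "we hope to observe a decrease in h-AKI with the intervention". The section then says that between unexposed and exposed AKI patients "differences could be expected, if incidence of h-AKI should be influenced by the intervention differentially in specific subgroups of the hospitalised population", and gives a shift towards older patients as its example.

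**Response in the mortality analysis.** Model-3, the primary result, adjusts for period, age, gender, Charlson score and possibly ethnicity. The stated reason for the patient covariates is imbalance between hospitals and steps. Neither AKI stage at first alert nor h-AKI status enters the model.

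**Other relevant analyses.** Secondary outcomes 1 and 3 model h-AKI incidence and stage-specific AKI incidence, with overnight admissions as denominator. Table-2 shows admissions and AKI episodes by hospital and period. Table-3 shows AKI levels, h-AKI share and 30-day deaths by hospital and exposure. Data from hospitals offers a remedy for changed detection after a laboratory re-organisation, but only for the incidence analysis.

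**The concern.** Whether an episode is counted is settled after exposure has begun, most clearly for h-AKI. Two routes can change the counted group. Prevention removes episodes, and the plan aims for this. More frequent creatinine testing, once alerts are visible and staff trained, could add mild episodes. Running the same algorithm in both phases fixes how a blood result is classified, not how often blood is taken.

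Either route changes the denominator of the primary outcome, and demographic and comorbidity adjustment cannot restore it. A lower odds of death per flagged episode might then reflect added mild cases. A null result might hide a benefit if mainly low-risk episodes were prevented. The sample size section converts its target effect into deaths avoided per year, and that conversion holds only if the flagged group stays the same.

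**Working it through.** **1. The plan's own figures.** Inputs from Sample size calculation: "total annual admissions of about 434,000", AKI in 2.5% of admissions, 30-day mortality 16% falling to 12.8%.
- Episodes per year: 434,000 × 0.025 = 10,850. Per hospital per quarter: 10,850 / 5 / 4 = 542.5, which agrees with "average of AKI episodes per hospital per 3 months of about N=540".
- Power: Hussey-Hughes variance with categorical period, random hospital effect, transition cells dropped, 540 episodes per cell, difference 0.032 and two-sided 5% (sidedness assumed). Cells before each hospital's transition were taken as control, as the text describes, although Table-1 as shown codes them as exposed after the second period. With variance at the mean rate of 14.4% and the ICC as a share of total variance, power is 79.0%, 80.2%, 82.2% and 86.4% at ICC 0.01, 0.05, 0.10 and 0.20. The stated 80% is reproduced.
- Deaths: 10,850 × 0.032 = 347 per year, against the plan's figure of around 300.

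**2. Extra detection, no death averted.** Let x be the extra flagged episodes as a fraction of the original number, and q their mortality. Both are assumptions; the SAP gives neither. Observed mortality = (0.16 + x·q) / (1 + x).

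| x | q | Observed mortality |
|---|---|---|
| 5% | 8% | 0.164 / 1.05 = 15.6% |
| 5% | 4% | 0.162 / 1.05 = 15.4% |
| 20% | 8% | 0.176 / 1.20 = 14.7% |
| 20% | 4% | 0.168 / 1.20 = 14.0% |

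The apparent fall runs from 0.38 to 2.0 points, which is 12% to 62.5% of the 3.2-point target (0.38 / 3.2 and 2.0 / 3.2).

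**3. Chance of a significant reduction from this alone.** Same design, variance at 16%, ICC 0.01 to 0.2: about 5% for x = 5%, q = 8%; 13-15% for x = 10%, q = 5%; 33-39% for x = 20%, q = 5%. The nominal rate in that direction is 2.5%. These are large-sample figures for a trial with five clusters.

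**4. Prevention.** Let s be the fraction of episodes prevented and q the mortality those episodes would have had (both assumed). Mortality among the rest = (0.16 − s·q) / (1 − s).
- s = 10%, q = 5%: 0.155 / 0.90 = 17.2%.
- s = 10%, q = 30%: 0.130 / 0.90 = 14.4%.

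The direction turns on whether the prevented episodes carry less or more than 16% mortality. The rate is the same whether those patients live or die without AKI.

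**5. Would the incidence analyses reveal a shift?** At 540 episodes per cell the standard error of the log rate ratio is about 0.033. Power is about 82% for a 10% change in all AKI and nearly 100% for 20-25%. For a subset holding half the episodes it is about 53% for a 10% change and 97% for 20%. Over-dispersion and small-cluster corrections are ignored, so these figures are optimistic.

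**6. Behaviour of AKI deaths per admission.** With no death averted, extra detection raises this measure by x·q / 0.16: from 0.05 × 0.04 / 0.16 = 1.25% to 0.20 × 0.08 / 0.16 = 10%. If prevented cases die without AKI, it falls by s·q / 0.16: 3.1% for s = 10%, q = 5%, and 18.75% for s = 10%, q = 30%.

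**The case against.** Four points can be made for the plan.

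- **A shift would not go unseen.** A reader might infer that nothing planned would expose a change in the AKI group. The SAP does not support that. Extra mild cases should raise stage 1 incidence, prevention should lower h-AKI incidence, and Tables 2 and 3 show the numbers, stage mix and h-AKI share. Crude AKI deaths per admission could be worked out from them. This stands, but such results only warn: they do not say how much of a mortality difference is selection.
- **The plan does not claim constant case numbers.** Its sentence concerns people who present with AKI, and it states the hoped-for fall in h-AKI immediately afterwards. This stands, so the sentence needs qualifying, not deleting.
- **Extra testing is an inference.** The SAP nowhere says that alerts or training raise testing. A reader might conclude that the primary result is biased towards benefit; neither the presence nor the direction of a bias is established. What stands against the plan is that it does not consider testing frequency.
- **The supportive analyses are imperfect.** Restriction to early alerts does not remove extra testing early in the stay. AKI deaths per admission still counts only flagged patients, so it can hide a benefit or create a false one (step 6). This is why neither should be able to overrule the primary result.

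The laboratory re-organisation remedy is a separate matter, since such a change is not an effect of the intervention.

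**Conclusion.** The point holds in a limited form. The plan acknowledges that the exposed AKI group may differ, but its mortality analysis answers with covariates that carry neither severity nor mode of detection, and no supportive mortality analysis addresses the selection. Existing outputs would flag a shift without separating it from a true effect.

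On assumed inputs, dilution alone could produce 12% to 62.5% of the target difference with no death averted. Prevention could push the rate up or down. These are illustrations of scale, not estimates: they rest on the plan's 16% mortality and on assumed numbers and mortality of added or removed episodes. The stated sample size and power are not in question here.

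**What to change.** Keep Model-3 as the primary result and pre-specify two supportive analyses. Both use data already requested: hours from admission to first alert, 30-day death, and admissions per period.

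1. **Model-3 restricted to episodes first flagged within 24 h of admission.** State that this largely removes selection by inpatient prevention but not by extra testing early in the stay.
2. **Deaths within 30 days of an AKI alert per overnight admission.** Analyse hospital-period counts with admissions as offset, treatment and period terms, and allowance for over-dispersion, which the planned incidence model does not include. State that this measure cannot fall merely because mild cases are added, but that it can rise with extra detection and fall if prevented cases die without AKI. The requested data list no deaths for admissions without AKI.

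Report both beside the primary result with these limits, and interpret any mortality benefit in their light, with no formal veto.

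Qualify the sentence on people presenting with AKI: a common algorithm does not fix how often creatinine is tested. If a laboratory-link change occurs, apply the exclusion of newly detectable episodes to the mortality analysis too, as a separate sensitivity check.

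Cost: two further analyses and a few sentences, with no new data. The first uses fewer episodes, and the second is less precise.
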